## **Evaluation of the Wisdom Enhancement Timeline Approach for Post-Stroke Depression Using a Single-Case Experimental Design**

[name]1a, [name], [name]

**Date:** 26/03/2024

This study will aim to answer the question: *Does enhancing wisdom through the timeline technique improve mood in post-stroke depressed individuals?* Additionally, it will examine whether enhancing wisdom restores identity continuity and improves self-esteem.

It is hypothesised that wisdom will improve first, followed by gains in identity clarity or self-esteem, as structured self-reflection fosters agency and self-worth. Finally, mood regulation is expected to improve last, aligning with findings that emotional stabilisation follows meaning-making and self-affirmation rather than occurring simultaneously (Beaumont, 2009).

### **Methods**

#### **Design**

A single-case experimental multiple-baseline design (MBD) will be adopted. Following Christ's (2007) recommendations, the study will pre-specify hypotheses, predetermine baseline durations, and randomise allocation via Random.org. Participants will be assigned to baseline durations of 2, 3, or 4 weeks, with non-concurrent intervention introduction to enhance flexibility. The independent variable will be the intervention, and the dependent variables will be mood, wisdom, identity, and self-esteem, measured repeatedly. Blinding will not be implemented due to feasibility constraints.

Although stability is generally recommended before intervention, Krasny-Pacini and Evans (2018) suggest that five baseline data points are sufficient to distinguish natural fluctuations from intervention effects. Replication will be built into the multiple-baseline design, with each participant serving as an independent test of the intervention's effects. Initially, a one-month follow-up review will be planned; however, this may be omitted if time does not permit.

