#### **Participants**

Three participants will be recruited, meeting SCED standards (Epstein et al., 2021; Kratochwill et al., 2013) through local stroke services. Inclusion criteria will require adults with post-stroke depression (PSD) who can provide informed consent and engage in therapy. Exclusion criteria will include severe cognitive or mental health impairments, medical instability, substance dependency, concurrent psychological treatment, participation in clinical trials, or newly prescribed psychotropic medication that has not yet stabilised. Participants who start psychotropic medication during the trial will remain eligible, as SCED analysis can account for medication-related changes.

NHS clinical teams will identify eligible participants, seeking permission for the researcher to contact them, while the author will conduct eligibility assessments and deliver the intervention. After the baseline phase, participants will attend six weekly sessions, either in person at a hospital or online via video conference.

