#### **Measures**

Participants will receive a measure pack containing all measures, along with questions on medication use and adverse events.

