#### **Idiographic Visual Analogue Scale**

The primary outcome will be assessed using a Visual Analogue Scale (VAS), a widely used measure

for tracking subjective experiences in clinical research (McCormack et al., 1988). Participants will rate their agreement with four daily statements on vertically presented 10 cm scales, with higher scores indicating stronger agreement. VAS items will be aligned with the research questions and reviewed for relevance by individuals with lived stroke experience via the university's Personal and Public Involvement (PPI) database.

The four VAS items will be:

1. Today, my mood is good (VAS\_mood)
2. Today, I feel able to accept the person I am/Today, I feel like I am adapting to life after my stroke (identity; VAS\_ID)
3. Today, I feel good about myself (self-esteem; VAS\_SE)
4. Today, I feel that I can use the wisdom of my life to help me deal with my current problems (VAS\_wisdom)

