### **Analysis**

Both single-case visual and statistical techniques will be used following best practices (Harrington & Velicer, 2015; Manolov & Moeyaert, 2017). Visual analysis will assess phase variability using a  $\pm 25\%$  stability envelope (Lane & Gast, 2014). Higher percentages will indicate greater stability, and lower percentages will reflect greater variability.

To assess whether VAS ratings during the intervention phase are higher than baseline, Tau-U (Parker et al., 2011) will be implemented. It will account for baseline trends, effect sizes, and phase non-overlap. Resistant to autocorrelation, Tau-U provides strong statistical power in small datasets (Parker et al., 2014). Interpretations will follow Vannest and Ninci's (2015) guidelines, with baseline corrections applied as needed to prevent inflated effect sizes.

Piecewise regression (Center et al., 1985) will complement Tau-U findings by quantifying change over time within each phase. Level and slope changes will be examined, estimating the breakpoint for outcome improvements. This approach will model level shifts and gradual trends while considering data variability and abrupt changes (Tate & Perdices, 2018).

To address autocorrelation, lag-1 autocorrelation will be assessed, and if detected, Generalised Least Squares (GLS) regression with an AR(1) structure will be applied (Somer et al., 2022).

Reliable change in PHQ-9 will be measured via the Reliable Change Index (RCI; Jacobson & Truax, 1991), with Cronbach's  $\alpha = 0.79$  (De Man-Van Ginkel et al., 2012) and a stroke sample SD of 5.1 (Strong et al., 2021). Clinically Significant Change (CSC) will not be determined due to limited non-clinical-normative data for stroke populations. Given concerns about the comparability of PHQ-9 scores between stroke and non-stroke populations (Blake et al., 2025), data from other populations will not be considered. Instead, a cut-off of 10 will be applied to approximate clinically meaningful change, based on validated studies (De Man-Van Ginkel et al., 2012; Negeri et al., 2021; Williams et al., 2005).

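### Blinding is waived for every role, although outcome labels could be masked for the analysis decisions that bear on the hypothesised order of change

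*Combined protocol and SAP*

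**What the plan says.** The Design section of the combined protocol and SAP disposes of masking in one sentence: "Blinding will not be implemented due to feasibility constraints". It gives no reasoning by role.

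The other relevant statements are:

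- **Therapist.** Under Participants, "the author will conduct eligibility assessments and deliver the intervention".
- **Primary outcome.** It is self-rated: "Participants will rate their agreement with four daily statements on vertically presented 10 cm scales". The items cover mood, identity, self-esteem and wisdom.
- **Handling of forms.** Under Measures, "Participants will receive a measure pack containing all measures, along with questions on medication use and adverse events". Who collects, scores or sees the packs is not stated.
- **Hypothesis.** The opening section predicts that wisdom improves first and identity or self-esteem next. It then says "Finally, mood regulation is expected to improve last".
- **Analysis.** Tau-U is to be used "with baseline corrections applied as needed to prevent inflated effect sizes". Piecewise regression is to estimate when each outcome starts to improve. Visual analysis uses a ±25% stability envelope. No analyst, second rater or coding of series is described.

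**The concern.** Feasibility is a sufficient reason for leaving participants and therapist unblinded. It is not an evident reason for leaving outcome names in view when analysis decisions are taken.

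The study's distinctive claim is about sequence. Whether wisdom moves before mood depends on how the breakpoint is estimated in each series. Whether each outcome improved at all depends partly on whether a baseline trend is corrected. If those choices are made knowing which series is wisdom and which is mood, they can drift towards the predicted order without any intention to do so. A reader of the report could not tell whether that had happened.

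Separately, an unqualified waiver leaves out the main limitation of unblinded self-report: participants' ratings may change because therapy has begun, whatever its content.

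**Working it through.** The plan gives no figure on this point to reproduce. The check is mainly textual, with two short calculations.

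**1. Who could be masked, and to what**

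| Role | What the plan says | Can it be masked? |
|---|---|---|
| Participant | rates own state daily | No; knows when therapy starts |
| Therapist | the author | No, as to phase |
| Analyst | not stated | Yes, as to outcome name |

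The waiver covers all three rows; feasibility is evident only for the first two.

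**2. Which decisions are open**

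- Baseline correction: no trigger is given.
- Breakpoint: it is to be estimated, but no rule is given for how, or for what counts as one outcome preceding another.
- Visual analysis: the envelope is numeric, so less is open here.

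The number of series is 3 participants × 4 items = 12.

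**3. How far one open decision can move Tau-U**

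Assumptions: complete daily ratings, giving baselines of 2, 3 or 4 × 7 = 14, 21 or 28 points; 6 × 7 = 42 intervention points; and the form of Tau-U that subtracts the baseline trend score from the between-phase score and divides by n_A × n_B. The plan does not state which form it uses.

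The baseline trend score is τ_A × n_A(n_A − 1)/2, where τ_A is Kendall's tau within baseline. Correction therefore changes Tau-U by τ_A × (n_A − 1)/(2 n_B):

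- n_A = 14: τ_A × 13/84 = 0.15 τ_A
- n_A = 21: τ_A × 20/84 = 0.24 τ_A
- n_A = 28: τ_A × 27/84 = 0.32 τ_A

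The coefficients are upper limits, reached only if the baseline rises without a single reversal (τ_A = 1). A weaker trend gives a proportionally smaller change. This sizes one decision in one series; it does not estimate bias.

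**4. Whether the staggered baselines deal with expectancy**

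Staggering protects against events tied to calendar time or to elapsed time. A change in reporting that begins when therapy begins moves with the stagger and would recur in each participant.

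For a pure reporting shift of d SD and no true effect, expected Tau = 2Φ(d/√2) − 1. The chance of p < 0.05 in one participant was simulated with a two-sided Mann-Whitney test (4,000 runs per setting, 14, 21 or 28 baseline points and 42 intervention points):

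| Assumed d | Expected Tau | Independent ratings | Lag-1 correlation 0.3 |
|---|---|---|---|
| 0 | 0 | about 5% | 13–14% |
| 0.25 | 0.14 | 11–18% | 19–25% |
| 0.5 | 0.28 | 34–51% | 38–52% |
| 0.8 | 0.43 | 69–87% | 65–82% |

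The shift sizes are assumptions. The table shows only that a phase comparison cannot separate such a shift from a treatment effect. It says nothing about what masking outcome labels would gain, because label masking does not act on participants' expectancy.

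**The case against.** **The limitation is disclosed, and most of the analysis is numeric.** This is largely true. The only visual criterion named is a stability envelope, and conclusions about effect rest on Tau-U and regression. What remains open is when to correct the baseline and how to settle the breakpoint. A fixed numeric rule for correction would close the first gap more directly than masking. It is compatible with masking and would not settle the breakpoint.

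**Coding the series cannot hide everything.** Also true. Baselines of different length can reveal the participant, and phase stays visible. Participant identity should in any case remain available, because the plan relies on the analysis to account for medication started during the trial. Only the outcome name needs to be hidden, and that is what the ordering hypothesis turns on.

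**Stronger readings that a reader might draw, and that the documents do not support:**

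- *The ratings should be withheld from the therapist.* The pack also carries medication and adverse-event questions, no one is documented as able to receive and check forms daily, and keeping a depressed patient's ratings from the person treating them is a debatable clinical trade-off. Participants' own expectancy would remain.
- *The treating author analyses the data with names in view.* The plan is silent on who analyses. The criticism is the silence.
- *A wish to please acts on the intervention phase only.* The author meets participants at eligibility assessment, before treatment. Contact increases with therapy but does not start there.

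**Conclusion.** The point holds as a modest, inexpensive improvement. The waiver is wider than its stated reason supports: outcome labels can be masked at analysis, and the plan combines open analysis decisions with a directional prediction about which outcome moves first. All 12 VAS series are affected.

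The size of any bias cannot be derived from the documents. Under the form of Tau-U assumed above, the choice to correct a baseline moves the estimate by at most 0.15 to 0.32 in a single series, and by less for ordinary baseline trends. Assumed reporting shifts must not be read as the benefit of masking.

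The conclusion rests on two inferences: that a co-author can hold a code key (the title page shows three authors), and that silence about the analyst means no safeguard is planned. Label masking protects the ordering claim and the correction decisions. It leaves participant expectancy untouched, and that should be stated as a limit on the causal conclusion.

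**What to change.** Replace the blinding sentence in Design, with a matching entry in Analysis, so that the plan states:

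1. Participants and therapist are unblinded. Say who sees the ratings and who analyses them.
2. An existing co-author prepares a coded file in which the four VAS outcome names are removed and their order is randomised within each participant. Participant and phase may stay identifiable, so that medication changes can still be linked.
3. Visual-analysis, baseline-correction and breakpoint decisions are made and recorded on that file before the codes are broken, preferably by a team member who neither delivered therapy nor entered the ratings.
4. Participants' expectancy in self-rated outcomes starts with therapy, is not removed by the staggered baselines, and limits the causal conclusion.

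The cost is one coded data file and a co-author to hold the key. The protection is weaker if the treating author is also the analyst, since a series may then be recognised; in that case the plan should say so. No change to treatment, visits or measures is needed.

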#### **Participants**

Three participants will be recruited, meeting SCED standards (Epstein et al., 2021; Kratochwill et al., 2013) through local stroke services. Inclusion criteria will require adults with post-stroke depression (PSD) who can provide informed consent and engage in therapy. Exclusion criteria will include severe cognitive or mental health impairments, medical instability, substance dependency, concurrent psychological treatment, participation in clinical trials, or newly prescribed psychotropic medication that has not yet stabilised. Participants who start psychotropic medication during the trial will remain eligible, as SCED analysis can account for medication-related changes.

NHS clinical teams will identify eligible participants, seeking permission for the researcher to contact them, while the author will conduct eligibility assessments and deliver the intervention. After the baseline phase, participants will attend six weekly sessions, either in person at a hospital or online via video conference.

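### Participants who start psychotropic medication are kept because the analysis is said to handle it, but no planned analysis uses the medication data, and Tau-U would credit an intervention-phase drug effect to therapy

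*Combined protocol and SAP*

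**What the plan says.** All references are to the combined protocol and SAP.

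- **Participants, entry.** Exclusions include "newly prescribed psychotropic medication that has not yet stabilised".
- **Participants, after entry.** "Participants who start psychotropic medication during the trial will remain eligible, as SCED analysis can account for medication-related changes".
- **Measures.** The pack holds the outcome measures "along with questions on medication use and adverse events". The text does not say how often the medication question is asked or whether a start date is recorded.
- **Analysis, Tau-U.** Its purpose is "To assess whether VAS ratings during the intervention phase are higher than baseline", "with baseline corrections applied as needed to prevent inflated effect sizes".
- **Analysis, piecewise regression.** It complements Tau-U: "Level and slope changes will be examined, estimating the breakpoint for outcome improvements". GLS with an AR(1) structure follows if autocorrelation is found.
- **Analysis, PHQ-9.** "Reliable change in PHQ-9 will be measured via the Reliable Change Index", together with a cut-off of 10.
- **Design.** The intervention is the only independent variable named, and there is no blinding. Three participants are planned, each treated as a separate test of the intervention.

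**The concern.** The plan treats an unstabilised new prescription as a reason to exclude at entry, and accepts the same exposure after entry because the analysis is said to deal with it. The Analysis section names adjustments for baseline trend and for autocorrelation only. It has no medication covariate, sub-phase, truncation at the start date, sensitivity analysis or reporting rule.

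What is at stake is attribution. A drug started during the intervention phase raises later ratings in the same phase as the therapy, and a phase contrast cannot tell the two apart. With three participants, one affected case is a third of the evidence. If the handling is chosen after unblinded data have been seen, it is less credible than a rule written now.

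**Working it through.** The plan states no sample size, power or alpha, so it has no figure of its own to reproduce. The check has two parts.

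**1. Which planned analysis uses the medication answers?**

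| Analysis | What it uses | Uses medication? |
|---|---|---|
| Stability envelope | Spread of ratings within phase | No |
| Tau-U | Baseline v intervention, baseline trend | No |
| Piecewise / GLS AR(1) | Level, slope, breakpoint, lag-1 correlation | No |
| PHQ-9 RCI and cut-off | Pre and post scores | No |

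**2. What does this do to the results if a start occurs?**

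Inputs from the documents: daily VAS ratings, baselines of 2, 3 or 4 weeks (nA = 14, 21, 28), and six weekly sessions, taken as nB = 42 days. Assumptions not in the documents: no therapy effect, a drug effect of 1 within-person SD with immediate onset unless stated, lag-1 autocorrelation of 0 or 0.3, and a two-sided 5% test.

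*Expected Tau.* A rating raised by 1 SD contributes 2Φ(1/√2) − 1 = 0.52 against a baseline rating. Only post-start ratings are raised:
- start after 7 ratings: 35/42 × 0.52 = 0.43
- start after 14 ratings: 28/42 × 0.52 = 0.35

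*Significance threshold.* Var(S) = nA·nB·(nA + nB + 1)/3, and the threshold for Tau is 1.96·√Var/(nA·nB):
- nA = 14: Var = 14·42·57/3 = 11172; SD of Tau 0.180; threshold 0.352
- nA = 21: Var = 21·42·64/3 = 18816; SD 0.156; threshold 0.305
- nA = 28: Var = 28·42·71/3 = 27832; SD 0.142; threshold 0.278

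The expected 0.43 exceeds all three thresholds. The expected 0.35 is about at the first and above the other two.

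*Simulated share significant in favour of the intervention* (ranges over nA and autocorrelation):

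| Setting | Start after 7 ratings | Start after 14 ratings |
|---|---|---|
| 1 SD, immediate | about 69-91% | about 50-72% |
| Same, baseline-corrected | 67-87% | 49-66% |
| 1 SD, building over 14 days | 52-74% | 31-49% |
| 0.5 SD, immediate | 26-40% | 16-29% |

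With no drug the share is 2-8%. Tau restricted to baseline plus pre-start intervention ratings gives 2-7% under the drug scenario. These are positive-tail rates, so the nominal value is 2.5%. At autocorrelation 0.3 the two-sided rate with no drug is already 12-15%, which is a separate weakness of Tau.

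The baseline correction changes little because it subtracts trend within baseline, and an intervention-phase start leaves the baseline untouched.

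*Piecewise model, break fixed at the phase switch.* At intervention day 21 the bias is 0.65-0.84 SD (immediate) or 0.53-0.69 SD (gradual). Standard errors are 0.87-2.35 SD, and the bias is below one standard error in every setting.

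*Adding a medication term.* With the right onset shape the bias goes to zero. A step term for a gradual effect leaves 0.42-0.52 SD, and a ramp term for an immediate effect leaves 0.11-0.42 SD. Standard errors are then 0.95-2.5 SD.

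*Start 7-10 days before the switch.* Piecewise bias is −2.6 to −0.7 SD if immediate and −1.1 to +0.5 SD if gradual, so even its sign depends on the unknown onset. Baseline-corrected Tau favours the intervention in both cases (0.11-0.33 and 0.35-0.45). For a same-day start, a step term duplicates the phase term and cannot be estimated.

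**The case against.** The strongest reply is that the design already holds what is needed: daily ratings, staggered baselines, replication, an estimated breakpoint, and a statement that the piecewise approach considers abrupt changes. A start may also never happen. Part of this stands. The consequence is conditional, and the piecewise analysis is fairly robust. But the reference to abrupt changes is generic, neither the breakpoint nor the plots are assigned to check medication, and replication across participants does not repair the affected one. Tau-U is the analysis named for testing whether ratings rise.

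A reader might infer four stronger points that the documents do not support.

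- *A drug effect on mood would reproduce the hypothesised sequence*, since "mood regulation is expected to improve last". The hypothesis also requires earlier gains in wisdom and then in identity or self-esteem. A drug effect on mood alone would not produce those, so the ordering across the four VAS items is a partial safeguard.
- *The piecewise results are compromised as well.* For intervention-phase starts with the break fixed at the switch, the bias is below one standard error. Bias was not assessed with the breakpoint estimated, as the plan intends.
- *A medication covariate solves the problem.* The wrong-shape residuals and large standard errors show otherwise.
- *Affected participants should not be counted, or should need a minimum number of pre-start ratings.* The plan has no counting rule across participants, and this would add a new criterion. Power figures are a weak basis for a minimum, because Tau is not a valid 5% test at autocorrelation 0.3.

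**Conclusion.** The concern holds as a gap between a stated property and the written analysis: the plan relies on an adjustment for medication that the Analysis section does not contain. That conclusion rests on the text alone and is firm. The harm falls mainly on Tau-U, and on the pre-post PHQ-9 change, which has no time series from which to separate the two effects.

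The size is illustrative. Under a 1 SD immediate drug effect and no therapy effect, a false finding for therapy rises from 2-8% to roughly 50-91% of series, depending on when the drug starts and on baseline length. Smaller or slower drug effects reduce this, to 16-40% for 0.5 SD immediate. The point should be fixed before data are analysed. It does not call the eligibility rule or the design into question.

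**What to change.** Leave eligibility and clinical management as they are, and write the accounting into the Analysis section.

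1. Record the start date of any psychotropic medication on the existing medication question, and mark it on the plots.
2. For a start in the intervention phase, pre-specify Tau-U on baseline plus pre-start intervention ratings as a sensitivity analysis, reported beside the full-series result.
3. For a start in baseline or close to the phase switch, state that drug and therapy effects cannot be reliably separated, and report that participant's result as not attributable to therapy alone. Report the PHQ-9 reliable change of any affected participant in the same way.
4. Reword the sentence in Participants so that it points to this analysis, and Participants, Measures and Analysis agree.

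A medication term in the piecewise/GLS model may be added as description only.

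The cost is wording plus one date on a form already in use. Truncated Tau-U is less precise. With a 4-week baseline and 14 pre-start ratings, Var = 28·14·43/3 = 5619, so the SD of Tau is 0.191 against 0.142 with all 42. With a 2-week baseline and 7 pre-start ratings, Var = 14·7·22/3 = 719, so it is 0.274 against 0.180. A non-significant truncated result should therefore not be read as absence of a therapy effect. Attribution is weaker for an affected participant, and if one is affected, two unconfounded replications remain.
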